## **Sample Size Determination**

Number of patients per group was determined from a pre-study power analysis using previously published data on prevalence of PTA after pilon fracture – the assumption being that a 10% reduction in percentage of patients experiencing symptomatic PTA would be clinically significant.

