Title: Does early platelet rich plasma injection decrease the risk of post-traumatic arthritis in pilon fractures undergoing two-staged open reduction with internal fixation?

Protocol version: 1.3

Protocol date: 08/30/2016

Principal Investigator: [name]

NCT: 02481869

A) Scientific Aims

Specific Aim 1: Determine the effects of a single intra-articular injection of platelet rich plasma (PRP) for mitigating the development of post-traumatic arthritis (PTA) in patients being surgically treated for pilon fractures in one ankle.

Null hypothesis: A single intra-articular injection of platelet rich plasma (PRP) will not be associated with significant improvements in outcome based on patient-reported measures of pain and function, as well as diagnostic imaging findings of PTA in patients being surgically treated for pilon fractures in one ankle.

Specific Aim 2: Assess the discriminatory potential of a synovial fluid biomarker panel for categorizing presence and severity of PTA based on patient-reported outcome measures of pain and function, as well as diagnostic imaging findings in patients being treated for pilon fractures in one ankle.

Null hypothesis: Synovial fluid biomarkers will not have high discriminatory capabilities for categorizing presence and severity of PTA in patients being treated for pilon fractures in one ankle.

B) Background and Significance

Pilon fractures are common and are associated with a 75% chance for symptomatic post-traumatic arthritis (PTA).¹ Although the mechanisms for initiation and progression of PTA after pilon fracture are incompletely understood, articular fracture is known to induce pro-inflammatory cytokines and degradative enzymes, which can result in chondrocyte death, accelerate cartilage degradation, and drive synovitis after injury. These pathologic processes appear to be especially important in the early phases of disease.²⁻⁴ Current treatments for articular fractures are focused on biomechanical issues: anatomic reduction, rigid stability, and limb alignment. These are critical issues to address for optimal healing, early limb use, and joint function. However, the biologic components of articular fracture are likely as, or even more important, with respect to development of PTA. As such, research efforts also need to focus on these important aspects in order to mitigate the development and progression of joint pathology after articular fracture.

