In an in vitro study, antioxidant treatment delivered hours after articular cartilage injury was reported to prevent progression of PTA-related pathology.⁵ Using canine models of PTA, our group has noted significant benefits after intra-articular injection of platelet rich plasma (PRP) in decreasing pain, improving limb use, maintaining joint range of motion, and mitigating progression of osteoarthritis. Beneficial results associated with PRP treatment of OA have also been reported in clinical veterinary patients.⁶ Based on this translational evidence in conjunction with the regulatory status and availability of PRP for clinical use in trauma patients, this orthobiologic therapy appears to have strong potential for providing a practical means of mitigating development of PTA in patients suffering ankle fracture. Importantly, we will be able to use a synovial fluid biomarker panel that has been shown to have high discriminatory potential for categorizing presence and severity of OA in dogs⁹, to assess patients for PTA after pilon fracture – which provides critical data regarding disease mechanisms^{7,8} – and treatment monitoring for development and assessment for novel therapeutic strategies for this pervasive problem.

C) Previous Work on the Study

There has been little published work on this particular treatment strategy for post traumatic arthritis of the ankle

D) Methods

With IRB approval and informed consent, patients (n=40) will be included who sustain closed pilon fracture of one ankle and are undergoing initial reduction with spanning external fixation, followed by open reduction with internal fixation (ORIF). Up to 50 patients will be enrolled in order to account for expected attrition in this patient population. Patients will be randomized to one of two treatment groups:

- PRP (n=20): single intra-articular injection of 5 ml of a leukocyte-reduced platelet rich plasma (ACP, Arthrex, Naples, FL) at the time of closed reduction and initial stabilization using ankle-spanning external fixation

- Control (n=20): single intra-articular injection of 5 ml of sterile 0.9% saline at the time of closed reduction and initial stabilization using ankle-spanning external fixation

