Study candidates will be identified as they present to the University Hospital emergency room or clinics and will be recruited for enrollment. Informed consent will be obtained as per IRB protocol. The patients will be approached by an orthopedic resident physicians, attending, or study staff to present the current study. Patients will be told of the details of the study and what is required of them if they chose to participate. The patients will be randomized by envelope to one of two groups, the PRP or control group. The patients will be blinded to which treatment they receive. Patients will be treated according to current standard of care, Following initial reduction and placement of ankle-spanning external fixation, synovial fluid will be aseptically obtained via arthrocentesis from both ankles and saved for subsequent biomarker analysis at the Comparative Orthopedic Laboratory. For the injured ankle, the PRP injection will be performed through the same needle used for arthrocentesis. PRP will be isolated from venous blood drawn from a peripheral vein. When appropriate, ORIF will be performed for definitive fracture treatment likely 7-14 days following external fixator placement. Prior to capsulotomy for ORIF, synovial fluid will again be aseptically obtained via arthrocentesis from both ankles and saved for subsequent biomarker analysis.

Follow-up assessments will be performed at 3 weeks, 6 weeks, 12 weeks, 6 months, 12 months, and 18 months after surgery for all patients. Radiographs will be obtained at 6 weeks and each subsequent visit. Patient reported outcomes (PRO) including AOFAS, SF 12 and VAS for pain and level of function will be recorded at all follow-up assessments starting at 3 weeks. At 18 months, MRI of the affected ankle will be performed and used for whole-joint assessment of OA.¹⁰

Number of patients per group was determined from a pre-study power analysis using previously published data on prevalence of PTA after pilon fracture – the assumption being that a 10% reduction in percentage of patients experiencing symptomatic PTA would be clinically significant. Patients and all patient evaluators will be kept blinded to treatment until all data are collected and analyzed by the co-investigator responsible for

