## **Data Analysis**

For data analysis, PTA presence will be defined based on a diagnosis of OA, or findings consistent with OA, reported for either imaging modality at any assessment time point. PTA severity will be determined from whole-joint MRI scoring and patient reported outcomes at 18 months after surgery and categorized as mild, moderate or severe. To test the first hypothesis, we will compare treatment groups for statistically significant ( $p < 0.05$ ) differences in proportions with PTA, proportions within each severity category, and PRO scores using Fisher's exact tests, t-Tests, and rank sum tests. To test the second hypothesis, we will perform receiver operator characteristic curve analyses to determine the discriminatory capabilities (area under the curve (AUC)) of the panel for distinguishing the presence and severity of PTA. The injured ankle will be compared to the normal, contralateral ankle and  $AUC > 0.8$  will be considered to represent high and clinically useful discriminatory capability. In addition, patient age, gender, BMI, tobacco use, and co-morbidities, as well as the pre-operative CT scan injury severity score will be assessed as variables for predicting likelihood of presence and severity of PTA using Fisher's exact test and odd's ratios.

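### The 20 patients per group are attributed to a power analysis for a 10% reduction in symptomatic PTA, but the planned two-sided Fisher test has at most 7.3% power for a 10-point reduction at that size

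*SAP*

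**What the plan says.** Protocol section D (Methods) and the SAP section Sample Size Determination carry the same statement. It opens by naming the source of the size: "Number of patients per group was determined from a pre-study power analysis using previously published data on prevalence of PTA after pilon fracture". The effect behind that analysis is then given as "the assumption being that a 10% reduction in percentage of patients experiencing symptomatic PTA would be clinically significant". Neither paragraph gives the calculation, the target power, the control rate, the sidedness, or whether 10% is absolute or relative.

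The other relevant statements are:

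- **Size.** Protocol section D plans 20 patients on PRP and 20 on saline, and adds: "Up to 50 patients will be enrolled in order to account for expected attrition in this patient population".
- **Prevalence.** The only figure is in Protocol section B, which says pilon fractures are "associated with a 75% chance for symptomatic post-traumatic arthritis (PTA").
- **Test.** The SAP section Data Analysis, like Protocol section D, compares the groups at p < 0.05 for "differences in proportions with PTA, proportions within each severity category, and PRO scores using Fisher's exact tests, t-Tests, and rank sum tests".
- **Endpoint.** The same section states: "PTA presence will be defined based on a diagnosis of OA, or findings consistent with OA, reported for either imaging modality". A finding at any of the visits counts.

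**The concern.** A trial of 40 patients comparing two proportions can detect only very large differences, so a stated basis of a 10% reduction called for a check. If 20 per group does not follow from that assumption, the documents credit the design with a property it lacks.

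What is at stake is how the PTA comparison will be read. Someone who takes the sample-size paragraph at face value would treat a non-significant result as evidence against a clinically important reduction. The trial could not support that reading, although it could argue against very large effects.

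There is a second mismatch. The 10% and the 75% both describe symptomatic PTA, while the tested variable is an OA diagnosis or OA findings on imaging. No expected rate is given for that variable.

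**Working it through.** **Inputs from the documents.** 20 per group, and 25 per group if all 50 enrolled are analysed (Protocol D). Significance level 0.05 and Fisher's exact test (SAP Data Analysis; Protocol D). 10% reduction (SAP Sample Size Determination; Protocol D). 75% prevalence (Protocol B).

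**Assumptions.** Two-sided testing, since the plan tests for differences. 80% target power. 75% as the control rate, then varied. Where a range of control rates is shown, 50% to 95% is my assumption.

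**1. Trying to reproduce 20 per group.** The pooled-variance formula without continuity correction is

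n = [1.960 × √(2·p̄·(1−p̄)) + 0.8416 × √(p₁(1−p₁) + p₂(1−p₂))]² / (p₁−p₂)²

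For 75% vs 65%, p̄ = 0.70:

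- 1.960 × √0.42 = 1.270
- 0.8416 × √(0.1875 + 0.2275) = 0.542
- n = (1.270 + 0.542)² / 0.01 ≈ 328.5, so 329 per group

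| Assumed control rate | 10 points absolute, n per group | 10% relative, n per group |
|---|---|---|
| 50% | 388 | 1565 |
| 75% | 329 | 571 |
| 90% | 199 | 240 |
| 95% | 141 | 152 |

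These normal-formula sizes are slightly too small for Fisher's test, which reaches 80% power for the absolute reduction at about 404, 347, 214 and 151 per group. One-sided testing at 80% power from 75% to 65% still needs 259. The most favourable case, 100% to 90% (or 10% to 0%), needs 74 per group two-sided and 58 one-sided. No variant gives 20.

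**2. Power at the planned size.** I enumerated every pair of outcomes (21 × 21 tables at 20 per group, 26 × 26 at 25), marked those with two-sided Fisher p < 0.05, and summed their binomial probabilities.

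| Scenario | 20 per group | 25 per group |
|---|---|---|
| 75% vs 65% | 6.1% | 6.6% |
| 75% vs 67.5% | 4.4% | 4.6% |
| 10 points, best control rate | 7.3% | 8.6% |
| 10% relative, control 50% to 95% | 2.7% to 6.4% | 4.4% to 7.1% |

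The lowest power for a 10-point reduction at 20 per group is 4.3% (100% vs 90%). With no true difference, at 75% in both groups, the test rejects 2.4% of the time at 20 per group.

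**3. Sensitivity to the test.** At 20 per group and a 10-point reduction, one-sided Fisher reaches at most 11.2% (10.6% from 75%). An uncorrected Pearson chi-square test reaches at most 15.4% (11.0% from 75%).

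**4. What the design can detect.** Reduction giving 80% power, two-sided Fisher:

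| Assumed control rate | 20 per group | 25 per group |
|---|---|---|
| 50% | 42 points | 39 points |
| 75% | 48 points | 41 points |
| 90% | 43 points | 38 points |
| 95% | 39 points | 34 points |

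**5. What a result would look like.** These are exact unconditional 95% confidence intervals for control minus PRP, obtained by inverting two one-sided score-ordered tests. With 15/20 vs 13/20, exactly a 10-point reduction, the interval is about −19 to +38 points. With 15/20 in both groups it is about −28 to +28 points, so even identical groups leave a 10-point reduction well inside the interval.

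**The case against.** The strongest reply is that no printed sum is wrong. The documents show no calculation, and 10% might be only a threshold of clinical relevance, with the study powered for some larger effect in an analysis kept on file. That reading is weak. The sentence says the power analysis determined the number per group and presents the 10% as its assumption, and neither document offers another effect size. If such an analysis exists, the remedy is to state it.

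Other points, and what stands of each:

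- **The 7.3% ceiling is conditional.** It assumes a two-sided test, 20 per group and 10% read as points. This is correct and should be said. The alternatives above raise power to 15.4% at most at 20 per group, far below any usual target.
- **The 75% is not a rate for the tested endpoint.** Also correct, which is why every control rate was scanned. The conclusion does not rest on 75%.
- **The normal-formula sample sizes are not Fisher sizes.** True. They understate the Fisher requirement by about 4% to 8%, so the correction widens the gap.
- **PTA is not named as the sole primary outcome.** Aim 1 also covers pain and function scores. This point makes no claim about them, since no effect size is given for them. The sample-size paragraph, however, rests on PTA alone.
- **An exact confidence interval is a reporting preference.** Its absence is not itself an inconsistency. It is proposed because it shows directly what the trial can and cannot exclude.

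**Conclusion.** The concern holds, and the paragraph must be corrected. No reading of the stated inputs supports 20 per group. For a 10-point reduction, power is 4.3% to 7.3% whatever the control rate, and at most 8.6% if all 50 patients are analysed. From 75% to 65%, the normal formula asks for 329 per group against 20 planned, a factor of about 16 (329 / 20 = 16.5). These figures assume two-sided testing at 0.05, and the required sizes assume 80% power; neither assumption is stated in the documents. The conclusion survives one-sided testing, a chi-square test, a relative reading of 10% and the larger enrolment. It concerns the PTA proportion only.

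**What to change.** In both places (Protocol section D and SAP Sample Size Determination), remove the claim that the number per group follows from a 10% reduction. The sponsor should state the actual basis for 20 per group. Then describe what the design delivers, for example:

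> With 20 evaluable patients per group and a two-sided Fisher's exact test at 0.05, 80% power requires a reduction in the proportion with PTA of about 39 to 48 percentage points, depending on the control rate (assumed 50% to 95%). Power for a 10-point reduction is about 4% to 7%. The published 75% concerns symptomatic PTA; the analysed endpoint is based on imaging and its expected rate is not known. The PTA comparison will be reported as a difference in proportions with an exact unconditional 95% confidence interval. A non-significant result will not be interpreted as absence of a 10% reduction.

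The cost is two reworded paragraphs and one added interval. The stated justification becomes less favourable, and the sponsor has to supply the real one. Enrolment, procedures and the planned tests are unchanged.

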## **Data Analysis**

For data analysis, PTA presence will be defined based on a diagnosis of OA, or findings consistent with OA, reported for either imaging modality at any assessment time point. PTA severity will be determined from whole-joint MRI scoring and patient reported outcomes at 18 months after surgery and categorized as mild, moderate or severe. To test the first hypothesis, we will compare treatment groups for statistically significant ( $p < 0.05$ ) differences in proportions with PTA, proportions within each severity category, and PRO scores using Fisher's exact tests, t-Tests, and rank sum tests. To test the second hypothesis, we will perform receiver operator characteristic curve analyses to determine the discriminatory capabilities (area under the curve (AUC)) of the panel for distinguishing the presence and severity of PTA. The injured ankle will be compared to the normal, contralateral ankle and  $AUC > 0.8$  will be considered to represent high and clinically useful discriminatory capability. In addition, patient age, gender, BMI, tobacco use, and co-morbidities, as well as the pre-operative CT scan injury severity score will be assessed as variables for predicting likelihood of presence and severity of PTA using Fisher's exact test and odd's ratios.

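### The t-tests and rank sum tests planned for PRO scores use only attenders at each late visit; a repeated-measures model would use data already collected and protect the 18-month comparison at little cost

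*SAP*

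**What the plan says.** In the SAP, Data Analysis, the first hypothesis is tested partly on "PRO scores using Fisher's exact tests, t-Tests, and rank sum tests", at a 0.05 level; the analysis text in Protocol section D repeats this. Neither place says at which visit or visits PRO scores are compared. Eighteen months is named only for the PTA severity category.

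Protocol section D sets the schedule: "Follow-up assessments will be performed at 3 weeks, 6 weeks, 12 weeks, 6 months, 12 months, and 18 months after surgery". The PROs (AOFAS, SF-12, VAS for pain and level of function) "will be recorded at all follow-up assessments starting at 3 weeks". No PRO before the injection is described.

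On numbers, section D states that "patients (n=40) will be included who sustain closed pilon fracture of one ankle", 20 to each arm, and then "Up to 50 patients will be enrolled in order to account for expected attrition in this patient population". No attrition rate is given. The available text contains no longitudinal model, missing-data rule or definition of the PRO analysis population. Part of the SAP was not available for review, so this is a statement about the text at hand.

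**The concern.** A two-sample test at a given visit needs a score at that visit. A patient who stops attending after 12 months drops out of the 18-month comparison, and that patient's five earlier scores cannot inform it. Enrolling extra patients restores the count, but not the randomised comparison if those who stay differ from those who leave in a way that differs by arm.

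At stake are the 18-month PRO difference and its nominal 5% error rate. The scores that could correct much of such a distortion are already collected under the protocol, but the named tests have no means of using them.

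**Working it through.** **Inputs from the documents.** Six PRO visits; target 40 (20 per arm); ceiling 50; level 0.05 (two-sided assumed). Implied loss: 50 − 40 = 10, and 10/50 = 20%. The reverse sum, 40/(1 − 0.20) = 50, agrees, but the 20% comes from the same ceiling, so this is no independent check. The plan gives no PRO effect size, SD or power figure to reproduce.

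**Assumptions, none of them in the documents.** 25 enrolled and 5 lost per arm; score SD 20; correlation ρ between 12- and 18-month scores of 0.5, 0.7 or 0.8; every leaver has a 12-month score; no treatment effect. Where leaving depends on score, the five patients in an arm ranking furthest in one direction on (12-month score + independent noise of SD 20) are lost.

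**Bias by formula.** The ranking variable correlates 1/√2 = 0.707 with the 12-month score. The mean of the lowest 20 of 25 standard normal values is about −0.336 (found by simulation). The 18-month mean among attenders in an affected arm therefore shifts by

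ρ × 20 × 0.707 × 0.336 = 2.4, 3.3 and 3.8 points for ρ = 0.5, 0.7 and 0.8.

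If both arms are affected in opposite directions, the shifts add: 4.8, 6.7 and 7.6 points. If they are affected in the same direction, the shifts cancel.

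**Simulation (5,000 to 6,000 trials per setting), t-test on attenders at 18 months.**

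| Leaving | Bias, points (ρ = 0.5 / 0.7 / 0.8) | Rejection at nominal 5% |
|---|---|---|
| Random | about 0 | about 5% |
| Depends on score, same rule in both arms | about 0 | 5% to 6% |
| Depends on score in one arm, random in the other | 2.4 / 3.2 / 3.9 | 7% / 9% / 10% |
| Depends on score, opposite directions by arm | 4.8 / 6.6 / 7.6 | 12% / 20% / 25% |

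In the opposite-direction case, a likelihood estimate using leavers' 12-month scores had a bias of −0.05, 0.05 and −0.05 points. If one rule applies to both arms but there is a true 10-point effect, the attenders-only difference is biased by about 1.0 to 1.6 points toward no effect.

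**Precision when leaving is random.** The attenders-only standard error is 20 × √(2/20) = 6.32. The likelihood estimate has variance smaller by the factor 1 − 0.20ρ² = 0.950, 0.902 and 0.872. The standard error ratio is its square root, 0.975, 0.950 and 0.934: reductions of 2.5%, 5.0% and 6.6%. Simulated standard errors were 6.39 against 6.22, 6.30 against 6.03, and 6.26 against 5.82.

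**Six visits.** A second simulation (2,000 trials per setting) spread about 20% dropout over all six visits, with exchangeable or autoregressive correlation. Opposite-direction leaving biased the attenders-only difference by 0.07 to 0.31 SD (×20 = 1.4 to 6.2 points); the likelihood estimate stayed within about 0.01 SD of the truth. Under random dropout the reduction in standard error ran from none (autoregressive, ρ = 0.5: 0.319 against 0.319 SD) to about 9% (exchangeable, ρ = 0.8: 0.319 against 0.291 SD). The gain depends on when patients leave and how correlation decays.

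**The case against.** The strongest reply is that the damaging scenario has little support. The protocol keeps patients and evaluators blinded. With working blinding and no treatment effect, nothing obvious makes patients leave for opposite reasons in the two arms. Under one common rule the error rate stays near 5%. This stands: rejection rates of 12% to 25% describe an extreme case, not what the trial should expect.

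Second, a reader might infer that the planned tests discard everything a withdrawn patient has reported. The documents do not support that. No section confines PRO testing to 18 months. If the tests are run visit by visit, a patient lost after 6 months still counts in four of the six comparisons. That reading does not remove the problem: each later comparison still rests on attenders alone, and up to six tests per scale at p < 0.05 add multiplicity.

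Third, ten losses are not a stated expectation. They follow from 50 minus 40, and the timing of loss is not given, so how many leavers will have several earlier scores is unknown. Those lost before 3 weeks will have none.

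Fourth, the near-zero bias of the likelihood estimate is partly built in, because in both simulations leaving depends only on observed scores plus noise. An unstructured covariance over six visits has 6 × 7/2 = 21 parameters for at most 50 patients and may not converge. Both points stand; they call for a stated fallback and a sensitivity analysis, not for keeping attenders-only tests as the main analysis.

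**Conclusion.** The point holds as an inexpensive improvement. The named tests cannot use earlier scores in a late-visit comparison, in a trial that collects six visits and expects attrition, and the SAP does not name the PRO visit to be compared. Under the assumed values, the distortion ranges from about zero (random leaving, or one rule in both arms with no effect), through about 2 to 4 points with 7% to 10% type I error (score-dependent leaving in one arm), to about 5 to 8 points with 12% to 25% in the extreme opposite-direction case. The standard error gain under random dropout is modest, about 2% to 7% when leavers have a 12-month score. The main reason to change is protection against bias. All sizes rest on assumed SD, correlation, loss and leaving mechanism. The documents do not show that the PRO comparison will be biased, only that the planned method has no protection if leaving depends on score and differs by arm.

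**What to change.** In the SAP, name the 18-month arm difference as the main contrast for each PRO. Estimate it with a mixed model for repeated measures with arm, visit and arm-by-visit terms, an unstructured covariance, and a specified simpler structure if that does not converge. Include all randomised patients with at least one follow-up PRO score, by assigned arm, rather than only those who reach 18 months. Keep the t-test or rank sum test on attenders as supportive.

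The model assumes that leaving is explained by observed scores. Add a sensitivity analysis that shifts leavers' values in both directions and separately by arm, since leavers may be doing better or worse than those who stay. Report how many patients in each arm were lost before 3 weeks; with no baseline PRO described, the model cannot recover them.

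The cost is a paragraph of SAP wording, one standard model per PRO and one sensitivity analysis. No new data are needed.

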all data analyses. For data analysis, PTA presence will be defined based on a diagnosis of OA, or findings consistent with OA, reported for either imaging modality at any assessment time point. PTA severity will be determined from whole-joint MRI scoring and patient reported outcomes at 18 months after surgery and categorized as mild, moderate or severe. To test the first hypothesis, we will compare treatment groups for statistically significant ($p < 0.05$) differences in proportions with PTA, proportions within each severity category, and PRO scores using Fisher's exact tests, t-Tests, and rank sum tests. To test the second hypothesis, we will perform receiver operator characteristic curve analyses to determine the discriminatory capabilities (area under the curve (AUC)) of the panel for distinguishing the presence and severity of PTA. The injured ankle will be compared to the normal, contralateral ankle and $AUC > 0.8$ will be considered to represent high and clinically useful discriminatory capability. In addition, patient age, gender, BMI, tobacco use, and co-morbidities, as well as the CT scan injury severity score¹¹ will be assessed as variables for predicting likelihood of presence and severity of PTA using Fisher's exact test and odd's ratios.

Based on its mechanisms of action and preliminary data, we expect to reject our null hypotheses and show that a single injection of PRP is associated with significant improvements in outcomes. We also expect that our synovial fluid OA biomarker panel will have high discriminatory capabilities for categorizing presence and severity of PTA in patients being treated for pilon fractures in one ankle.

Subject Selection

Inclusion criteria:

- Patients with closed unilateral pilon fractures
- Patients undergoing staged pilon procedures with an external fixator index procedure

Exclusion criteria:

- Patients who are younger than 18 years of age
- Open pilon fracture
- Patients with contralateral lower extremity injury
- Patients unable to comply with the follow-up appointments
- Patients who had previous ankle injury to the currently injured ankle
- Patients who are pregnant
- Prisoners

E) Re-consent of previously incompetent subjects

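### Aim 2's only benchmark (AUC > 0.8) sits with an injured-versus-normal-ankle contrast, which a marker of fracture alone can pass; the two ROC sentences must be reconciled

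*SAP*

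**What the plan says.** Protocol section A sets Aim 2 as "Assess the discriminatory potential of a synovial fluid biomarker panel for categorizing presence and severity of PTA". Its null hypothesis is "Synovial fluid biomarkers will not have high discriminatory capabilities for categorizing presence and severity of PTA".

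The SAP's Data Analysis section and Protocol section D (Methods) carry the same two ROC sentences. The first gives the AUC "of the panel for distinguishing the presence and severity of PTA". The second begins "The injured ankle will be compared to the normal, contralateral ankle" and goes on to say that an AUC above 0.8 "will be considered to represent high and clinically useful discriminatory capability". No other AUC criterion appears in either document, and no confidence interval or test goes with this one.

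Other relevant statements:

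- **Fluid sampling (Protocol D).** Draws are described twice, from both ankles each time: at external fixation, and before ORIF, likely 7-14 days later.
- **Other ankle (exclusion criteria).** "Patients with contralateral lower extremity injury" are not eligible.
- **PTA presence (SAP, Data Analysis).** It rests on OA findings "reported for either imaging modality at any assessment time point". Radiographs start at 6 weeks, and the side is not stated.
- **PTA severity.** It uses whole-joint MRI scoring and patient-reported outcomes at 18 months. The MRI is of the affected ankle only.

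**The concern.** The stated target and the benchmark point to different comparisons. The target is PTA status. The comparison named beside the benchmark is injured against uninjured ankle. At both described draws that is acute fracture against no fracture, in every patient.

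The Protocol's own background says "articular fracture is known to induce pro-inflammatory cytokines and degradative enzymes". A between-ankle difference is therefore expected whether or not the panel says anything about later PTA.

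An analyst who follows the benchmark sentence literally could report the panel as highly discriminating when it cannot separate injured ankles that develop PTA from those that do not. That would be a wrong answer to Aim 2. Two analysts could also reach opposite conclusions from the same data, because neither document names the ROC case and control groups or the role of the contralateral sample.

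**Working it through.** The 0.8 threshold is a chosen value with no inputs, and no sample size is stated for Aim 2, so there is no plan figure to reproduce. The check asks whether a marker with no PTA information can meet the benchmark.

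**Inputs.** From the Protocol: 40 patients with both ankles sampled, and a 75% symptomatic PTA rate. Assumed, because the documents give no marker data: one normal marker standing in for the panel, equal variances, a shift δ (in SD units) caused by fracture alone, between-ankle correlations of 0, 0.5 and 0.8, and PTA:no-PTA splits of 20:20, 30:10 and 35:5. The 30:10 split borrows the 75% rate (0.75 × 40 = 30), although that rate is for symptomatic PTA and the plan defines presence by imaging.

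**Step 1: expected AUC, injured versus contralateral.** AUC = Φ(δ/√2). Setting this to 0.80 gives δ = √2 × Φ⁻¹(0.80) = 1.414 × 0.8416 = 1.19 SD. For δ = 0.8, 1.0, 1.2, 1.5 and 2.0 the expected AUC is 0.714, 0.760, 0.802, 0.856 and 0.921.

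**Step 2: chance that the sample AUC exceeds 0.8.** Simulated with the Mann-Whitney AUC and at least 20,000 trials per setting; repeat runs agree to within about one percentage point.

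| Correlation | δ = 0.8 | 1.0 | 1.2 | 1.5 | 2.0 |
|---|---|---|---|---|---|
| 0 | 6% | 23% | 53% | 90% | >99.9% |
| 0.5 | 2-3% | 18% | 54% | 95% | 100% |
| 0.8 | 1% | 14% | 56% | 97% | 100% |

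**Step 3: the same marker, PTA versus no PTA among injured ankles.** All injured ankles share the shift, so it cancels. The mean AUC is 0.50. With 100,000 trials, the AUC exceeds 0.8 in 0.04%, 0.17% and 1.3% at 20:20, 30:10 and 35:5. Choosing the marker's direction from the data roughly doubles these rates and leaves the contrast unchanged.

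**Step 4: contralateral ankles as the no-PTA group.** Comparing only the injured ankles with PTA against contralateral ankles does not help. With shifts from 1.19 to 3 SD the mean AUC runs from 0.80 to 0.98, the same as for all injured ankles.

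**Step 5: precision of the contrast Aim 2 needs.** At A = 0.80 with m cases and n controls, Var = [A(1−A) + (m+n−2)(Q−A²)]/(mn). Q is the probability that two independent cases both exceed one control. Under equal-variance normals it is the bivariate normal probability at (0.8416, 0.8416) with correlation 0.5, which is 0.6872. The numerator is 0.16 + 38 × 0.04715 = 1.952 for every split of 40.

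| Split | Var | SE | 0.80 ± 1.96 SE | Logit-scale CI |
|---|---|---|---|---|
| 20:20 | 1.952/400 = 0.00488 | 0.070 | 0.66-0.94 | 0.63-0.90 |
| 30:10 | 1.952/300 = 0.00651 | 0.081 | 0.64-0.96 | 0.60-0.91 |
| 35:5 | 1.952/175 = 0.01115 | 0.106 | 0.59-1.00 (cut at 1) | 0.52-0.94 |

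The logit interval is ln 4 ± 1.96 × SE/0.16, transformed back.

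**The case against.** The strongest reply is that the target is already clear. The first ROC sentence introduces only an AUC for PTA. The benchmark's wording about discriminatory capability echoes the null hypothesis, which is about PTA. On that reading 0.8 governs the PTA AUCs and the contralateral ankle is a reference value. Severity grades also cannot be analysed by injured versus contralateral alone, so the authors must have intended some other ROC analysis. This reading is plausible and may be what was meant. But the text does not state it, and even if it is right, the groups compared and the role of the contralateral sample remain undefined.

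A second reply is that the simulation only confirms its own setup, and that pass rates run from 1% to 100% with the assumed shift. That stands: the figures show possibility, not likelihood.

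A third is that contralateral ankles could serve as no-PTA controls if both sides are radiographed. The side is indeed not stated, so the affected-side MRI settles severity but not presence. Step 4 shows, however, that such controls bring the fracture effect back.

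Finally, the replacement AUC may be too imprecise for a decision. That is also true, and it should be disclosed.

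**Conclusion.** The concern holds and should be fixed. The aim and the first ROC sentence target PTA, while the sentence with the only success criterion names a contrast that, at the described draws, separates fracture from no fracture. Read literally, the criterion can be met by a marker with a PTA AUC of 0.50 once fracture moves it by roughly 1.2 SD or more.

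That size rests on an assumed shift, normality, equal variances and one marker in place of the panel. The conflict between the sentences needs none of these. Confidence is medium because a benign reading exists. The effect is confined to Aim 2; the PRP versus saline comparison is untouched.

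**What to change.** Reconcile the two sentences in both documents by naming the ROC groups, the role of the contralateral sample, and the AUC to which 0.8 applies. Example wording:

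> ROC analyses will compare injured ankles with PTA against injured ankles without PTA (presence as defined above) and, among injured ankles, the 18-month severity grades (ordinal c-index or a stated cut). The 0.8 threshold applies to these AUCs, each reported with a 95% CI. Contralateral values will be used only to normalise within patient. Injured versus contralateral will be reported separately as an injury-response analysis.

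Normalisation is one possible role; if the sponsor intends another, the plan should state it and explain how fracture is kept apart from PTA. The plan should also account for treatment group when the pre-ORIF sample is used, because that sample follows the injection.

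The cost is wording plus analysis of samples and imaging already planned, with no new draws, visits or scans. The price is a less favourable and less precise AUC: with the intervals in Step 5, Aim 2 may support only a descriptive conclusion, and the plan should say so in advance.
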